### 3.7.5 *Acute Kidney Injury*

AKI will be measured at Day 1 and EOS. AKI will be defined as stage 1 or higher using modified RIFLE criteria ([Appendix D of protocol](#)) at any time within the first 7 days or new need for renal replacement therapy between Day 1 and EOS.

For Day 1 and EOS assessment per RIFLE criteria, the counts and percentage of subjects will be summarized based on categories: None, Risk (R), Injury (I), Failure (F), Loss (L), ESKD (E).

Proportion of subjects with AKI between Day 1 and EOS will be provided. Chi-square test p-value will be provided to compare AP-SA02 and placebo.

AKI will be derived based on any of below assessments:

- 1) AKI assessments with results RIFLE within first 7 days from the first dose date, or
- 2) New need for renal replacement therapy.

All AKI assessments will be listed by subject based on randomized subjects.

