 - a. At the time of positive SA blood culture was undergoing chronic intermittent hemodialysis or peritoneal dialysis;
 - b. Positive blood culture for SA after 2 or more days on anti-staphylococcal antibiotic treatment;
 - c. Temperature $\geq 38.0^{\circ}\text{C}$ (100.4°F) at ≥ 72 hours after initial blood culture;
 - d. SAB associated with signs or symptoms of metastatic foci and/or hematogenous seeding, including, but not limited to, septic thrombophlebitis, osteomyelitis (not including osteomyelitis associated with hardware or prosthetic joint infection), deep soft tissue abscess, septic arthritis/bacterial native joint infection, septic pulmonary emboli/infarction, visceral soft tissue abscess, or empyema confirmed by physical examination, imaging, or culture; and/or
 - e. Presence of right-sided SAB endocarditis (native valve) by modified Duke criteria ([Appendix C](#)), with no clinical evidence of cerebral foci requiring at least 28 days of anti-SA antibiotic treatment.

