7.2 Phase 2a Endpoints

The Phase 2a endpoints are the following:

- Time to reach a NEWS2 score ≤ 2 maintained for at least 24 hours or hospital discharge (whichever comes first) for subjects on active drug versus placebo in the Microbiological Intent-to-Treat (MITT) Population;
- Clinical Improvement or response at TOC for study drug (Day 12) in the MITT Population;
- Proportion of subjects reaching a NEWS2 score ≤ 2 maintained for at least 24 hours or hospital discharge (whichever comes first) for subjects on active drug versus placebo at TOC for study drug (Day 12) in the MITT Population;
- Microbiological outcome at EOT for study drug (Day 5);
- Clinical Improvement or response at TOC for BAT (7 days [± 1 day] after the end of BAT);
- Clinical Improvement or response at EOS (28 days after the end of BAT);
- Time to death;
- NEWS2 score while hospitalized by study day;
- Late composite efficacy, as defined by the following:
 - Survival at EOS (Days 39 to 81); and
 - No evidence of microbiological failure, as defined by either of the following:
 - Blood cultures that remain positive for SA ≥ 7 days from randomization; or
 - Isolation of SA from the blood or another sterile site (eg, joint fluid, tissue) > 14 days from randomization.

- Microbiological failure or relapse by any of the following:
 - Blood cultures that remain positive for SA ≥ 7 days from randomization;
 - Isolation of SA from the blood or another sterile site (eg, joint fluid, tissue) >14 days from randomization; or
 - Blood culture positive for SA >72 hours after the first blood cultures showing CL of SAB (defined as 2 consecutive days with negative SA blood cultures).
- Time to resolution of SAB;
- Time to hospital discharge (and time to hospital discharge readiness);
- Need for and duration of intensive care unit stay;
- Need for and duration of endotracheal mechanical ventilation;
- Need for and duration of noninvasive pressure ventilation (eg, Continuous Positive Airway Pressure, Bilevel Positive Airway Pressure);
- PK of AP-SA02 with IV administration;
- Relationship between AP-SA02 exposures and safety and efficacy endpoints;
- Immunogenicity of AP-SA02 at EOS;
- Time to resolution of any signs and/or symptoms of bacteremia present at Screening;
- Time to resolution of any signs/symptoms related to focal site of SA infection (eg, joint pain; redness; swelling; weight-bearing, back pain; weight-bearing, skin redness; drainage) from randomization on Day 1;

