8.7 Clinical Laboratory Evaluations

Blood samples for chemistry, hematology, coagulation, CRP, and procalcitonin will be obtained at Screening, daily from Day 1 through EOT for study drug (Day 5), Day 7, TOC for study drug (Day 12), TOC for BAT, and EOS. Clinical laboratory assessments will be performed post-dose after the second infusion on Day 1. All standard blood tests will be analyzed centrally by a certified clinical laboratory and details on the collection and processing of central laboratory samples can be found in the Laboratory Manual.

Following study drug dosing, the Investigator will review laboratory values for those outside of normal range and will be required to conduct clinically appropriate follow-up procedures. Clinical significance of the values outside of normal ranges will be assessed by the Investigator.

The analytes listed in [Appendix B](#) will be measured at Screening, daily from Day 1 through EOT for study drug (Day 5), Day 7, TOC for study drug (Day 12), TOC for BAT, and EOS.

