8.8 Acute Kidney Injury

AKI will be measured at Day 1 and EOS. AKI will be defined as stage 1 or higher using modified RIFLE criteria ([Appendix D](#)) at any time within the first 7 days or new need for renal replacement therapy between Day 1 and EOS.

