The Kaplan-Meier method will be used to estimate the 25%, median and 75% times. The hazard ratio, 95% confidence interval (CI) of hazard ratio, and p-value from Cox regression model will be provided to compare AP-SA02 and placebo. Cox regression will include treatment (AP-SA02 and placebo) as factor.

The Kaplan-Meier plot of time to hospital discharge (and time to hospital discharge readiness) will be provided.

Need for ICU stay will be summarized with counts and percentages of subjects. Chi-square test p-value will be provided for the counts of subjects who need ICU stay to compare AP-SA02 and placebo.

Duration of ICU stay during the study period from the Day 1 will be summarized with descriptive statistics for subjects who need for ICU stay.

The duration of ICU stay can be calculated as sum of each ICU stay from date of admission to date of discharge when the type of hospitalization is “ICU” in eCRF.

A t-test p-value will be provided for duration of ICU stay to compare AP-SA02 and placebo.

Need for endotracheal mechanical ventilation will be summarized with counts, and percentages of subjects. Chi-square test p-value will be provided for the counts of subjects who need endotracheal mechanical ventilation to compare AP-SA02 and placebo.

The type of oxygen delivery methods will be collected in eCRF, and the endotracheal mechanical ventilation will include types “*mechanical ventilation via tracheotomy*” and “*endotracheal tube*” in eCRF.

Duration of endotracheal mechanical ventilation will be summarized with descriptive statistics for subjects who need for endotracheal mechanical ventilation during the study.

Need for noninvasive pressure ventilation (e.g., continuous positive airway pressure, bilevel positive airway pressure) will be summarized with counts, and percentages of subjects. Chi-square test p-value will be provided for the counts of subjects who need noninvasive pressure ventilation to compare AP-SA02 and placebo. Noninvasive pressure ventilation includes oxygen delivery methods, i.e., nasal cannula, high-flow nasal cannula, nonrebreather face mask, CPAP mask, BiPAP mask, BiPAP hood and other which are collected in eCRF.

Duration of noninvasive pressure ventilation will be summarized with descriptive statistics for subjects who need for noninvasive pressure ventilation during the study.

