- v. Investigator will provide an assessment of whether additional imaging is needed for potential metastatic infection based on clinical signs/symptoms of SA infection.
- w. All subjects with an intravascular catheter present at admission that is not thought to be infected and is not planned on being removed within 3 days of randomization should receive an ultrasound to evaluate for the presence of an intravascular clot within 2 days of randomization unless this was done within 7 days prior to Screening.

x. All subjects will receive a TTE and/or TEE ECHO within 3 days of randomization unless this was done within 7 days prior to Screening. Subjects with endocarditis should have a follow-up TTE or TEE between Days 7 and 14. All effort should be made to perform this before administration of study drug.

y. All work-up for distant sites of metastatic infection and all decisions regarding source control procedures will be performed as per primary team. IV catheters known or suspected to be infected must be removed or changed as soon as possible within 72 hours after randomization. Sites should identify source control within 3 days; potential source or evidence of ongoing infection after 7 days may be considered a clinical failure.

z. AKI will be defined as stage 1 or higher using modified RIFLE criteria at any time within the first 7 days or new need for renal replacement therapy between Day 1 and EOS

aa. Serum for AP-SA02 anti-phage antibodies will be performed prior to the first dose.

bb. HIV antibody, HBsAg, and HCV antibody testing will be performed at Screening, only if status is unknown.

cc. FCBPs only must have a negative serum pregnancy test within 72 hours prior to randomization. Results can be from a local laboratory and will be confirmed at the central laboratory.

dd. A 12-lead ECG will be performed post first dose of the day.

ee. Assessments include chemistries, hematology, coagulation, CRP, and procalcitonin. See [Appendix B of protocol](#) for a list of clinical laboratory analytes.

ff. Clinical laboratory assessments and IL-10 will be performed post-dose after the second infusion.

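### The RIFLE part of the AKI endpoint rests on the Day 1 assessment alone and requires no worsening from baseline; separately, the SAP counts ordinary oxygen delivery as noninvasive pressure ventilation

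*SAP*

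**What the plan says.** **AKI.** Protocol 7.2 and 8.8 and SAP 2.3.2 and 3.7.5 define the endpoint in two parts: a RIFLE class in the first week, or new RRT between Day 1 and EOS. Footnote z of the SAP schedule (Appendix A) puts the first part this way: "AKI will be defined as stage 1 or higher using modified RIFLE criteria at any time within the first 7 days". On timing, Protocol 8.8 says "AKI will be measured at Day 1 and EOS" and SAP 3.7.5 agrees. The AKI row of both schedules marks only those two visits.

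SAP 3.7.5 then gives the derivation. The RIFLE limb is "AKI assessments with results RIFLE within first 7 days from the first dose date, or"; the other limb is "new need for renal replacement therapy". The section also tabulates Day 1 and EOS by category (None, R, I, F, L, E) and gives a chi-square p-value for AP-SA02 against placebo.

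One of the five Phase 2a qualifying conditions (Protocol 4.1, criterion 8a) is "At the time of positive SA blood culture was undergoing chronic intermittent hemodialysis or peritoneal dialysis". Creatinine and eGFR are in the chemistry panel (Protocol Appendix B), which Protocol 8.7 schedules at Screening and "daily from Day 1 through EOT for study drug (Day 5), Day 7, TOC for study drug (Day 12), TOC for BAT, and EOS".

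**Ventilation.** The Protocol 7.2 endpoint is "Need for and duration of noninvasive pressure ventilation (eg, Continuous Positive Airway Pressure, Bilevel Positive Airway Pressure"). SAP 3.4.1 makes it operational as follows: "Noninvasive pressure ventilation includes oxygen delivery methods, i.e., nasal cannula, high-flow nasal cannula, nonrebreather face mask, CPAP mask, BiPAP mask, BiPAP hood and other".

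SAP Section 6, which lists changes from the protocol, mentions neither derivation.

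**The concern.** The AKI definition covers a week, but the data named to feed it come from one day of that week. An assessment made on the first dosing day mostly describes the patient's renal state on entry. Injury that develops under treatment, and that the endpoint exists to find, enters only if it leads to RRT. Patients who arrive in renal failure may enter as events. The AKI proportion for each arm would then mix entry status with severe late outcomes, and the comparison between arms would be pulled towards no difference.

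The ventilation problem is separate and simpler. If a patient on a plain nasal cannula counts as needing pressure ventilation, the reported need and duration largely describe supplemental oxygen under another name.

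**Working it through.** The documents give no expected AKI or ventilation rate, so there is no planned figure to reproduce. The stated power concerns clinical response at Day 12 and is not touched by this point.

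**Step 1: schedule against window.**
- AKI assessments scheduled in Days 1-7: one (Day 1). In Days 2-7: none.
- The EOS assessment falls on Days 39-81, so it can never meet a 7-day rule.
- Chemistry days in Days 2-7: Days 2, 3, 4, 5 and 7, that is five. SAP 3.7.5 does not refer to them.

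**Step 2: RIFLE categories against window** (Protocol Appendix D, Table 8).
- Loss needs more than 4 weeks and ESKD more than 3 months. Neither can arise within 7 days of first dose, so any L or E counted by the RIFLE limb predates the drug.
- Failure can be met by creatinine of 4 mg/dL or more, with no change required.
- Risk and Injury are relative changes, but SAP 3.7.5 names no reference value.
- Table 8 has no numbered stages, so stage 1 is not mapped to a letter.

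**Step 3: are such patients enrolled?** Yes, through criterion 8a. The renal example in exclusion 16 covers only end-stage disease without a dialysis plan, and schedule footnote kk expects dialysis patients.

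**Step 4: illustration only.** Let d be the share on chronic dialysis, q the true new AKI on Days 2-7 among the rest, and r the share of new AKI that needs RRT. All three are assumptions. Assume also that every dialysis patient is scored E on Day 1 and nobody else has a Day 1 class. Then

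- AKI as derived = d + (1 - d) × q × r
- true new AKI = (1 - d) × q

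For the 42 planned Phase 2a subjects:

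| d | q | r | As derived | True new AKI |
|---|---|---|---|---|
| 0 | 20% | 10% | 42 × 0.020 = 0.8 | 42 × 0.200 = 8.4 |
| 10% | 20% | 10% | 42 × 0.118 = 5.0 | 42 × 0.180 = 7.6 |
| 20% | 10% | 10% | 42 × 0.208 = 8.7 | 42 × 0.080 = 3.4 |
| 30% | 5% | 10% | 42 × 0.3035 = 12.7 | 42 × 0.035 = 1.5 |

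The error can run in either direction. For the comparison between arms, take true new AKI of 30% against 10%, a risk ratio of 3:

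- d = 10%, r = 30%: (0.10 + 0.90 × 0.30 × 0.30) / (0.10 + 0.90 × 0.10 × 0.30) = 0.181 / 0.127 = 1.43
- d = 30%, r = 10%: (0.30 + 0.70 × 0.30 × 0.10) / (0.30 + 0.70 × 0.10 × 0.10) = 0.321 / 0.307 = 1.05

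These are the extremes over d = 10-30% and r = 10-30%.

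**Step 5: ventilation categories.** The SAP names six delivery methods plus an open one. Three deliver pressure in the sense of the protocol's examples: CPAP mask, BiPAP mask and BiPAP hood. Nasal cannula and nonrebreather mask do not fit. High-flow cannula is a definitional choice that the SAP should state. The open category could hold anything.

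**The case against.** The best defence on AKI is that Day 1 need not mean Day 1 only. Several items in the Day 1 column of the schedule (infectious disease consultation, ultrasound, echocardiogram, source control) carry their real window in a footnote. The AKI footnote speaks of the first 7 days, and the SAP derivation uses the plural for assessments. This leaves some room for a week-long reading, and unscheduled assessments could recover some cases. But neither document says so, and the timing sentence in Protocol 8.8 and SAP 3.7.5, together with the Day 1 and EOS tabulation, points the other way. At the least, the text needs settling.

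A reader might infer that the trial cannot detect renal injury. The documents do not support that. New RRT is captured through EOS. SAP 3.7.2 summarises chemistry at every scheduled visit, with post-baseline extremes, changes from baseline and comparisons between arms. Clinically significant laboratory abnormalities are reported as graded adverse events.

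A reader might also infer that the plan intends to score dialysis patients as acute injury. No passage says so. It is a consequence of applying the rule literally, and only through the RIFLE limb, since the other limb requires new need. Because patients are randomized, such counts are expected to dilute the comparison and not to favour an arm.

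Finally, AKI is one of many unranked Phase 2a endpoints, both documents disclaim formal testing, and the protocol gives CPAP and BiPAP as examples, not as a closed list. All of this stands. It limits the severity but does not make the two derivations match their endpoints.

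**Conclusion.** The point holds as a should-fix validity error in one safety endpoint, with a separate, smaller derivation error in the ventilation endpoint. On the plan as written, the RIFLE limb has one usable scheduled assessment and none on Days 2-7. It misses AKI in that period that does not reach RRT, and it can count renal failure that predates the first dose.

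The number of patients affected cannot be computed from the documents, which give neither a dialysis share nor an AKI rate. The counts and risk ratios in the illustration rest on assumed values and on literal scoring of every dialysis patient. They show that the error could be material, not that it has a known size. The conclusion depends on reading the timing statements as written; if a Day 1 form was meant to cover the whole week, the gap in onset would shrink, but the missing baseline rule would remain.

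**What to change.** **SAP 3.7.5**
- Derive RIFLE class programmatically from the creatinine/eGFR already scheduled through Day 7, using Protocol Appendix D.
- Compare with the last pre-dose value, consistent with SAP 3.1.2. This will normally be Screening, because Day 1 laboratory samples are drawn after the second infusion (footnote ff).
- Count only post-dose worsening to Risk or higher, and state that stage 1 means Risk (R).
- Report subjects on chronic dialysis, or in class L or E at baseline, separately from the at-risk group.
- Keep new RRT through EOS.

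**SAP 3.4.1**
- Restrict noninvasive pressure ventilation to pressure-delivering methods: CPAP mask, BiPAP mask and BiPAP hood.
- State how high-flow cannula is handled, and report other oxygen delivery separately.

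**SAP Section 6**
- List both changes. The AKI entry matters because the Day 1 and EOS timing comes from Protocol 8.8.

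The cost is SAP text and programming. The chemistry and oxygen-delivery data are already planned for collection, so no new data are needed.

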### 3.7.6 *Physical Examinations*

A complete physical examination will be performed at Screening, Day 7, TOC for study drug (Day 12), TOC for BAT, and EOS. A targeted physical examination will be performed daily from Day 1 through Day 6.

All physical examination data will be listed by subject based on randomized subjects.

### 3.7.7 Other Safety Assessments

Other assessments about echocardiogram, ultrasound assessments, and pregnancy test will be listed by subject based on randomized subjects.

Subjects with adverse events of endocarditis or endocarditis reported on echocardiogram will be listed by subject based on randomized subjects.

## 4 DATA REVIEW COMMITTEE

The DRC will convene throughout the study to review blinded safety data to recommend if it is safe and appropriate to continue the study as planned. The DRC will convene to recommend if dose selection and/or dose duration are appropriate prior to dose escalation during or after Phase 1b. Additionally, the DRC can receive unblinded data, if requested and deemed necessary to adequately complete their review. Further details regarding the roles, responsibilities, and procedures of the DRC will be provided in the DRC Charter.

## 5 INTERIM ANALYSIS

No interim analysis is planned.

## 6 CHANGES FROM PROTOCOL-SPECIFIED STATISTICAL ANALYSES

- 1) 'Time to resolution of SAB' is updated to 'Time to initial resolution of SAB' in Section 2.3.2.
- 2) The definitions of ITT, MITT, PK population, and Phage-Sensitive ITT Population are updated in Section 3.2.
- 3) 'Phage Persistence and Clearance Population' is added in Section 3.2.
- 4) The efficacy analysis and PD analysis conducted in Phase 1b based on ITT Population are added in Section 3.4 and Section 3.6
- 5) The efficacy analysis and PD analysis conducted based on Persistence and Clearance Population are added in Section 3.4 and Section 3.6.
- 6) 'Persistent SAB on 2 blood cultures obtained over 72 hours prior to study drug administration' and 'Foci of infection present at Screening' are added for subgroup analysis in Section 3.4.2.

## 7 PROGRAMMING SPECIFICATIONS

Analyses will be performed using SAS® version 9.3 or higher. Detailed Programming Specifications will be provided in a separate document.

**APPENDIX A. SCHEDULE OF PROCEDURES**

	Screening	Treatment Period a							TOC for Study Drug	TOC for BAT	EOS b	ETOT Visit
Day (±Visit Window)	-3 to -1 c	1	2	3	4	5	6	7	12 (±1 day) d	18-60 (±1 day) e	39-81 (±1 day)	U
Informed consent f	X											
Inclusion/exclusion criteria g	X											
Demographic information	X											
Medical/surgical history h	X											
Prior/concomitant medications	X i	X	X	X	X	X	X	X	X	X	X	X
Weight and height j	X											
Complete physical examination k,l	X							X	X	X	X	X
Targeted physical examination l,m		X	X	X	X	X	X					
Vital signs n	X	X o	X o	X o	X o	X o	X	X	X	X	X	X
NEWS2 score p		X	X	X	X	X	X	X	X			X
Blood cultures q	X	X	X r	X r	X r	X	X r	X	X	X	X	X r
Sterile site cultures	X s	X s	X s	X s	X s	X s	X s	X s	X s	X s	X s	X s
Infectious disease consultation		X t										
Signs/symptoms of SA infection u	X	X	X	X	X	X	X	X v	X	X	X	X
Assessment of clinical outcome									X	X	X	X
Ultrasound		X w										
ECHO		X x										
Source control y		X										
AKI assessment z		X									X	
Serum for AP-SA02 anti-phage antibodies		X aa						X	X		X	
IL-10	X	X ff	X	X	X	X	X	X	X			X
Serology testing bb	X											
Pregnancy test cc	X	X								X	X	X
12-lead ECG	X	X dd		X		X			X	X	X	X
Clinical laboratory evaluations ee	X	X ff	X	X	X	X		X	X	X	X	X
Urinalysis kk	X	X				X		X	X	X	X	X
PK blood sampling gg		X	X	X	X	X	X					
Urine samples for phage CL hh, kk		X						X	X	X		X
Randomization		X										
Study drug administration ii		X	X	X	X	X						
Adverse events jj	X	X	X	X	X	X	X	X	X	X	X	X

Note: Blood samples may be collected and stored for future assessments.

a. Daily visits will be performed at an inpatient location. Study days may not correspond exactly with calendar days during the Treatment Period. Additional dosing days will repeat procedures on Days 2 to 4, depending on the number of days added. The final day of dosing will mirror Day 5.

- b. EOS will occur 28 days after the end of BAT.
- c. The screening period will be up to 3 days. Subjects should be randomized as soon as possible after confirmation of study eligibility and can be randomized on the same calendar day as Screening.
- d. TOC for study drug will occur on Day 12. A  $\pm 1$  day window will be allowed if the subject is discharged.
- e. TOC for BAT will occur 7 days ( $\pm 1$  d) after the end of BAT.
- f. Signed informed consent by the subject (or LAR) must be obtained before any study-related procedures are performed.
- g. Subjects must continue to meet eligibility criteria at randomization.
- h. Relevant medical/surgical history will be collected. Any updates since the Screening Visit will be assessed at randomization.
- i. All relevant medications received in the 28 days prior to randomization must be recorded.
- j. Height will be collected at the Screening Visit only and will be used to calculate body mass index.
- k. A complete physical examination will include evaluation of HEENT, neck, lungs, heart, chest, abdomen, extremities, neurologic status, skin for evidence of emboli, palpation for signs of pain, and any other notable conditions.
- l. Pain on a physical examination should trigger diagnostic testing for metastatic foci of infection.
- m. A targeted physical examination will include evaluation for complications of bacteremia, HEENT, lungs, heart, skin for any evidence of septic emboli, and palpation for signs of pain.
- n. Vital signs will include temperature, heart rate, and blood pressure. Vital signs will be obtained at every visit unless the subject has been discharged and visits are being performed remotely. Wherever possible, vital signs will be obtained after at least 5 minutes resting in a supine or sitting position. If more than 1 measurement is taken on a given day, the highest value for temperature should be recorded in the eCRF.
- o. During the Treatment Period, vital signs should be obtained prior to each infusion (-1 hour window).
- p. A NEWS2 score will be recorded once per day (and should be repeated if there is a change in clinical status) from Day 1 through Day 7 and TOC for study drug (Day 12). NEWS2 is an aggregate scoring system derived from 6 physiologic parameters: respiration rate; oxygen saturation; systolic blood pressure; pulse rate; level of consciousness or new confusion, and temperature. The NEWS2 score will be calculated programmatically from the NEWS2 parameters entered in the eCRF; additional NEWS2 assessments should be repeated that day if indicated due to a change in clinical status.
- q. Two sets of blood cultures, preferably from 2 different sites, 30 minutes apart will be drawn on Day 1 as close to the start of study drug administration as possible, unless blood cultures have already been sent that day for Screening or clinical care. Thereafter, 1 set of blood cultures is acceptable. Blood cultures should be collected from a peripheral venipuncture site when possible until 2 consecutive days of negative blood cultures are obtained or otherwise clinically indicated. Repeat blood cultures will also be obtained at EOT for study drug (Day 5), Day 7, each of the TOC (BAT and study drug) and the EOS Visits, regardless of clinical indication, to evaluate for microbiological cure and sustained cure. See [Section 7.7](#) for additional details.
- r. Blood cultures will be drawn on these days, only if necessary, until 2 consecutive days of negative blood cultures are obtained or if clinically indicated.
- s. Sterile site cultures will be collected on these days as clinically indicated.
- t. All subjects will receive an infectious disease consultation within 2 days of randomization unless consultation was obtained prior to enrollment. If consultation can only be obtained after 2 days of randomization, this is permissible, but must be documented. Sites without access to an infectious diseases specialist must discuss with the Medical Monitor or Sponsor if the subject can be included in the study. If the Investigator specialty is infectious disease, a separate consultation is not required.
- u. Signs/symptoms related to focal site of SA infection (eg, joint pain; redness; swelling; weight-bearing, back pain; weight-bearing, skin redness; drainage) will be assessed at Screening, daily from Day 1 through Day 7, at TOC for study drug (Day 12), TOC for BAT, and EOS.
- v. Investigator will provide an assessment of whether additional imaging is needed for potential metastatic infection based on clinical signs/symptoms of SA infection.
- w. All subjects with an intravascular catheter present at admission that is not thought to be infected and is not planned on being removed within 3 days of randomization should receive an ultrasound to evaluate for the presence of an intravascular clot within 2 days of randomization unless this was done within 7 days prior to Screening.

x. All subjects will receive a TTE and/or TEE ECHO within 3 days of randomization unless this was done within 7 days prior to Screening. Subjects with endocarditis should have a follow-up TTE or TEE between Days 7 and 14. All effort should be made to perform this before administration of study drug.

y. All work-up for distant sites of metastatic infection and all decisions regarding source control procedures will be performed as per primary team. IV catheters known or suspected to be infected must be removed or changed as soon as possible within 72 hours after randomization. Sites should identify source control within 3 days; potential source or evidence of ongoing infection after 7 days may be considered a clinical failure.

z. AKI will be defined as stage 1 or higher using modified RIFLE criteria at any time within the first 7 days or new need for renal replacement therapy between Day 1 and EOS

aa. Serum for AP-SA02 anti-phage antibodies will be performed prior to the first dose.

bb. HIV antibody, HBsAg, and HCV antibody testing will be performed at Screening, only if status is unknown.

cc. FCBPs only must have a negative serum pregnancy test within 72 hours prior to randomization. Results can be from a local laboratory and will be confirmed at the central laboratory.

dd. A 12-lead ECG will be performed post first dose of the day.

ee. Assessments include chemistries, hematology, coagulation, CRP, and procalcitonin. See [Appendix B of protocol](#) for a list of clinical laboratory analytes.

ff. Clinical laboratory assessments and IL-10 will be performed post-dose after the second infusion.

gg. Venous blood samples for PK analysis of AP-SA02 levels will be collected from subjects enrolled at predetermined/qualified PK sites on Day 1 (pre-dose [-60 minutes], 0.5 hours [ $\pm 15$  minutes], 1 hour [ $\pm 15$  minutes], 3 hours [ $\pm 15$  minutes] post first dose of the day), Days 2 to 4 (1 sample 1 hour [30 minutes] post first dose of the study day, Day 5 (1 hour [ $\pm 15$  minutes] post last dose of the day), Day 6 (24 hours [ $\pm 30$  minutes] post last dose).

hh. Urine for phage CL will be collected prior to the first dose on Day 1, Day 7, TOC for study drug (Day 12), TOC for BAT, and ETOT. Date and time will be recorded for each urine sample collection at the designated time points.

ii. AP-SA02 or placebo will be administered via IV bolus infusion every 6 hours for 5 consecutive days in an inpatient location, unless the dose, frequency, or duration is modified after DRC review. In addition, all subjects will receive at least 14 days (uncomplicated SAB) or 28 days (complicated SAB) and up to 56 days of BAT. BAT will be administered at the discretion of the Investigator. Subjects must be directly observed during study drug/placebo administration by clinical personnel. The first dose of study drug on Day 1 must occur as close as possible to the time of randomization.

jj. Adverse events will be collected from the time of informed consent.

kk. It is expected that subjects enrolled who are also receiving dialysis (hemodialysis or peritoneal dialysis) may produce little or no urine. In such cases, urine for urinalysis or urine for phage clearance may not be available for collection at some or any of the timepoints listed in the protocol. Protocol deviations will not be issued for missed urine collections due to anuria.

AKI = acute kidney injury; BAT = best available therapy; CL = clearance; CRP = C-reactive protein; DRC = Data Review Committee; ECG = electrocardiogram; ECHO = echocardiogram; eCRF = electronic case report form; EOS = End of Study; ETOT = Early Termination of Treatment; FCBP = female of childbearing potential; HBsAg = hepatitis B surface antigen; HCV = hepatitis C virus; HEENT = head, eyes, ears, nose, and throat; HIV = human immunodeficiency virus; IL = interleukin; IV = intravenous(ly); LAR = legally authorized representative; NEWS2 = National Early Warning Score 2; PK = pharmacokinetic(s); RIFLE = Risk-Injury-Failure-Loss-End-stage renal disease; SA = Staphylococcus aureus; SAB = Staphylococcus aureus bacteremia; TEE = transesophageal; TOC = Test of Cure; TTE = transthoracic; U = unscheduled.
